11.2. Clinical Laboratory Tests

The tests outlined in the [Table 6](#) will be performed at the specified time points described in the Schedule of Activities.

Table 6: Clinical and Safety-related Laboratory Tests to be Performed

Hematology	Chemistry	Central Laboratory
WBC count	Glucose	Glucagon levels
RBC count	Creatinine	Insulin levels
Hemoglobin	Sodium	Immunogenicity
Hematocrit	Chloride	
Platelet count	Bicarbonate	
	Potassium	
	Calcium	
	Albumin	
	Alkaline Phosphatase	
	AST/SGOT	
	ALT/SGPT	

The local clinical laboratory at each site will perform all testing specified in Table 6 with the exception of Central Laboratory tests (i.e., plasma glucagon and insulin and immunogenicity testing). The investigator must maintain, on file, written evidence that the clinical laboratory to be used is certified under the Clinical Laboratory Improvement Act or equivalent certification (depending on local regulations). Further, the investigator must provide Xeris Pharmaceuticals or its agent with a copy of the certification, the range of normal values, the effective dates for the ranges, and the units of measurement for all laboratory tests requested in the protocol. If any of the laboratory measurements will be transformed and/or categorized in any way, a description of the procedures(s) used should be included. Xeris Pharmaceuticals or its agent must receive these documents before the shipment of clinical supplies.

One central analytical lab will analyze the glucagon and insulin samples, and another the anti-glucagon samples collected in this study. The procedures for preparing, storing and shipping these samples to the central analytical labs will be provided to each investigator prior to commencement of the study.

11.3. Vital Signs

Heart rate and respiration will be measured continuously by cardiorespiratory monitoring. These items along with BP and body temperature will be recorded in the CRF once daily at approximately the same time of day from Screening to the end of study treatment.

11.4. Photographs

Digital photographs of study drug infusion sites will be taken at the following times:

- Prior to the application of each OmniPod® pump, photograph the site of approximate cannula insertion.
- Upon removal of each OmniPod® pump, photograph the application site, paying particular attention to the cannula insertion site.

- For any insertion sites with Erythema or Edema scores >0 (Draize scale), follow-up photographs should be taken to document resolution.

Photographs should be time/date stamped and labeled with the subject ID number and stored on a secure, access-restricted computer. Care should be taken not to include the subject's face or other identifying information in the photographs.

12. SAFETY AND ADVERSE EVENT (AE) REPORTING

12.1. Adverse Events

All observed or volunteered AEs regardless of treatment group or suspected causal relationship to the study treatment will be reported. For all AEs, the investigator must pursue and attempt to obtain information adequate to determine the outcome of the AE and to assess whether it meets the FDA criteria for classification as an SAE (see Section 12.4) requiring immediate notification to Xeris Pharmaceuticals (see Section 12.9). For all AEs, follow-up by the investigator is required until the event resolves or stabilizes at a level acceptable to the investigator to consider it closed, and Xeris Pharmaceuticals should concur with that assessment.

As part of ongoing safety reviews conducted by the Sponsor, any non-serious adverse event that is determined to be serious (according to the FDA definitions of an SAE) will be reported by the Sponsor as an SAE. To assist in the determination of case seriousness, further information may be requested from the investigator to provide clarity and understanding of the event in the context of the clinical study.

12.2. Reporting Period

For all AEs, the reporting period to Xeris Pharmaceuticals begins from the time informed consent is obtained through the last administration of the investigational product.

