 - a. Using the same procedures for loading and weighing the pump, and confirming cannula deployment as detailed for Day 0, a new OmniPod® pump containing CSI-Glucagon™ solution should be placed immediately and again at least every 72 hours, including any time the pump alarms due to an occlusion.
 - b. Each time a pump is replaced, the safety of pump switch out procedures should be as assessed by occurrence of blood glucose < 50 mg/dL.
 - c. Each time a pump is removed, including at final termination of therapy, the pump should be weighed, and the placement site should be photographed and assessed with Draize scales and any reactions followed to resolution.
 - d. POC glucose will be assessed every three hours; or more frequently if the CGM shows glucose falling <70 mg/dL (3.9 mmol/L) or rising above >200 mg/dL (11.1 mmol/L). Additionally, the trajectory of change in plasma glucose concentration based on the two most recent POC measurements should be used to adjust the frequency of glucose monitoring as needed to prevent plasma glucose <70 mg/dL (3.9 mmol/L) or >200 mg/dL (11.1 mmol/L).
 - e. CGM will be utilized for rapid alerts, which will trigger POC assessments of blood glucose that will be used to guide clinical decisions. At least 2 hours prior to each planned pump change, confirm the CGM sensor is working and place another as needed.
 - f. Every 2 weeks during treatment, draw blood for immunogenicity testing.
7. Whenever CSI-Glucagon™ treatment is temporarily paused and when treatment ends:
 - a. Draw blood for CBC, CMP, immunogenicity testing and plasma insulin and glucagon.
 - b. Perform physical exam and measure height and weight.

- c. Resume IV fluids at pre-study rate and manage glucose as per standard procedures.

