10.2.4. Period 4, Post-treatment Immunogenicity Testing

At 28±14 days after receiving the last dose of glucagon in the study, subjects should have blood drawn for immunogenicity testing. Preferably, this will be done at the study site. If travel or other considerations preclude the subject returning to the study site, the blood draw may be performed at a local hospital, laboratory or clinic, or by home health care professional. In this case, the plasma sample will be sent directly to the central lab for testing. Xeris or its designee will coordinate with the site and the subject to facilitate collection, processing and shipping of this blood sample.

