Adverse events	—	—	x	x	x	x	

^a Update as applicable.

^b Complete only when treatment ends or pauses.

^c Normal clinical care samples drawn within 7 days of the intended start of Period 2 will satisfy this requirement.

^d To be drawn every 2 weeks during open-label treatment, Day 14 and 28 (if applicable), whenever treatment is paused, and at the end of open-label treatment.

^e Weekly or as needed.

^f Will be performed on Day 1 if subject is a treatment failure and is switched to open-label treatment at 24 hours.

^g To be drawn at 28 ±14 days post-glucagon treatment.

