12.9. Serious Adverse Event Reporting Requirements

If an SAE occurs, Xeris Pharmaceuticals is to be notified within 24 hrs. of awareness of the event by the investigator, regardless of the investigator’s determination of causality. In particular, if the SAE is fatal or life-threatening, notification to Xeris Pharmaceuticals must be informed as soon as possible, irrespective of the extent of available AE information. This time frame also applies to follow-up on previously forwarded SAE reports.

In the rare event that the investigator does not become aware of the occurrence of an SAE immediately (e.g., an outpatient study subject initially seeks treatment elsewhere), the investigator is to report the event within 24 hrs. after learning such event and document the time of first awareness of the AE.

A death occurring during the study, during the per-protocol follow-up period, or within 4 weeks after stopping treatment with test drug must be reported to Xeris Pharmaceuticals or its designee(s) immediately whether or not it is considered treatment-related. Initial SAE reports must be followed by detailed descriptions. These should include copies of hospital case records and other documents when requested. Telephone reports must be confirmed promptly either by email or overnight courier.

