12.13. Subject Monitoring

Subjects will be monitored for AEs throughout the study by the study unit staff. The principal investigator or designated sub-investigator will be on site for initial pump placement and for the subsequent 4 hours. The principal investigator or designated sub-investigator will also be on call for the remainder of the study. As necessary, a physician will administer treatment for any AEs.

Safety parameters, including laboratory results, will be assessed by the principal investigator or his delegate using the site's criteria for clinical laboratory acceptance ranges as suggested guidelines in making the medical assessment.

Scheduled safety measurements will be repeated according to appropriate SOPs or upon request from a physician. Any abnormal repeated measurement will be evaluated by a physician and repeated if judged necessary. Further action may be taken on the physician's request.

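### Section 12.2 closes all AE reporting at the last dose and Table 4 has no AE check in Period 4, so new non-fatal events after stopping have no clear collection route; the two also disagree on when AE collection starts.

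*Combined protocol and SAP*

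**What the plan says.** Section 12.2 sets one window for every AE: it "begins from the time informed consent is obtained through the last administration of the investigational product". It gives no separate window for SAEs.

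Table 4 has the AE row "Adverse events — — x x x x". Read against the column heads, this is a dash at Screening and at Day -1, a mark at Day 0, Day 1, Day 2 and each three-day open-label visit, and nothing under Period 4. The only Period 4 mark in the table is for immunogenicity.

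Section 10.2.4 plans a contact 28±14 days "after receiving the last dose of glucagon in the study, subjects should have blood drawn for immunogenicity testing". No AE enquiry is attached, and the sample may be taken away from the study site.

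When treatment pauses or ends, Section 10.2.3 tells the site to "Resume IV fluids at pre-study rate and manage glucose as per standard procedures".

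Three other provisions bear on the end of the window:
- Section 12.9: "A death occurring during the study, during the per-protocol follow-up period, or within 4 weeks after stopping treatment with test drug must be reported".
- Section 12.1: for all AEs, "follow-up by the investigator is required until the event resolves or stabilizes at a level acceptable to the investigator".
- Section 12.13: "Subjects will be monitored for AEs throughout the study by the study unit staff".

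**The concern.** Stopping a continuous glucagon infusion in an infant with hyperinsulinism is a moment when harm could appear. The protocol recognises this: Section 7.2 allows a taper when dosing ends for an SAE or a serious device injury, so that glucose support can be adjusted. Yet a hypoglycemic convulsion that begins after the final pump comes off is, on the wording of Section 12.2, past the end of reporting, while a death at the same time would be collected.

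The antibody sample raises the same difficulty. It is drawn after treatment without a question about clinical events, so a positive result could not be set against any late-onset reaction.

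At the other end, the definition of a treatment-emergent AE in Section 12.3 includes events already there before dosing that then become more frequent or worse. Applying it requires AE status before Day 0. Period 1 withdraws background drugs and weans IV glucose until readings below 70 mg/dL have occurred at least twice, so events there are plausible. A site working from Table 4 would not record them as AEs.

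**Working it through.** The plan gives no figure to reproduce here. The check is a comparison of sections followed by a day count.

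**Start of collection.** Section 12.2: consent. Table 4: Day 0. The difference is Screening plus Period 1.

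**End of collection.** Section 12.2: last dose. Table 4: last open-label visit. The two agree, so new-onset AEs have 0 days of stated collection after the last dose.

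**What is still captured after the last dose.**
- Deaths: to 4 weeks, and during per-protocol follow-up (12.9).
- AEs open at the last dose: until resolved or stable (12.1).
- Draize scores above 0 at pump removal: to resolution (10.2.2, 10.2.3, Appendix 1).
- Antibodies: at 28±14 days (10.2.4).
- Low glucose during a temporary pause or pump change: this precedes the last dose, so it stays inside the window. A pause that becomes permanent is the exception, because the dose before it is then the last.

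**What is left.** Non-fatal AEs and SAEs with first onset after final discontinuation.

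**Do other sections override the end date?** Section 12.13 refers to the whole study and to unit staff. The Synopsis and Section 7.1 describe three periods or phases, and the Synopsis gives a study length of up to 5 weeks (35 days) per patient. A subject treated for 28 days reaches Period 4 at 28 + 14 = 42 days at the earliest and 28 + 42 = 70 days at the latest. It is therefore unclear whether Period 4 counts as part of the study for Section 12.13, or as per-protocol follow-up for Section 12.9. The 24-hour SAE clock in Sections 12.4 and 12.9 says how quickly to report once aware; it sets no window and prompts no enquiry.

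**Size of the window.** Let E be days from first to last dose, taken as unbroken, and f the days from last dose to the Period 4 contact (28 − 14 = 14, 28, and 28 + 14 = 42). Share after last dose = f / (E + f).

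| Subject | E (days) | f = 14 | f = 28 | f = 42 |
|---|---|---|---|---|
| Full treatment | 28 | 14/42 = 33% | 28/56 = 50% | 42/70 = 60% |
| 24-hour responder stopping after the 4-hour open-label pump | 2 + 4/24 = 2.17 | 14/16.17 = 87% | 28/30.17 = 93% | 42/44.17 = 95% |
| 24-hour non-responder stopping at the same point | 1 + 4/24 = 1.17 | 14/15.17 = 92% | 28/29.17 = 96% | 42/43.17 = 97% |

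For deaths, the 4-week rule covers 28 days. If the draw falls on day 42, the last 42 − 28 = 14 days are covered only if Period 4 counts as per-protocol follow-up.

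**The case against.** The strongest reply is that the safety plan is much fuller than Section 12.2 read alone. Besides the routes listed above, the end of treatment brings a physical examination, hematology, chemistry, insulin, glucagon and antibody samples. Section 12.9 gives no end date for SAEs and even foresees a subject first treated elsewhere. IV fluids go back to the pre-study rate when treatment stops, which reduces the risk of hypoglycemia. Section 6.4.1 describes glucagon as very short-lived, so the risk from stopping it is unlikely to be spread over 14 to 42 days. Every subject may receive open-label glucagon, so late events offer no clean randomized comparison.

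Most of this stands, and it limits what can be claimed. It does not supply a route for a new non-fatal event: Section 12.2 is written for all AEs, and it is the only place that states an end date. The silence on SAEs in Section 12.9 is an ambiguity, not a window.

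A reader might go further and infer any of three things that the documents do not support:
- *Period 1 events are excluded from the safety data.* Under Section 12.2 they are included, because reporting opens at consent. The dashes in Table 4 conflict with that rule; they do not repeal it.
- *Worsening from baseline cannot be judged.* Table 4 schedules medical history, examination and laboratory tests at Screening, and vital signs and bedside glucose in Period 1, where glucose is checked at least every 3 hours. The weakness is in AE records specifically.
- *The whole post-dose period is unobserved, or all late reactions are lost.* The captured items above show otherwise.

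**Conclusion.** The point holds in a limited form. New-onset non-fatal AEs and SAEs after final discontinuation have no clear collection route, although a contact 14 to 42 days after the last dose is already planned. That interval is 33% to 60% of the time from first dose to contact for a subject treated for 28 days, and 87% to 97% for one who stops after the first open-label pump. These shares describe calendar time, not risk. The documents give no rate of post-dose events, so the number missed cannot be estimated, and events caused by stopping glucagon would probably cluster early in the interval.

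The conflict over the start of collection is a second, smaller defect: two parts of the protocol give sites different instructions, and the treatment-emergent definition depends on which is followed.

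The conclusion assumes that Section 12.2 governs where it differs from the general statement in Section 12.13, and that the blank Period 4 cell in the AE row means no assessment. The primary endpoint, sample size, power and type 1 error are unaffected. The change is worth making because it improves safety capture at very little cost.

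**What to change.** - **Section 12.2:** extend AE and SAE reporting through the existing Period 4 contact. The exact length is for the sponsor to settle, but it should be stated.
- **Sections 12.9 and 12.13:** align both with that window, and say whether Period 4 counts as part of the study and as per-protocol follow-up.
- **Table 4:** mark the AE row at Screening, Day -1 and Period 4.
- **Section 10.2.4:** add one AE question at the planned draw, or by telephone if the blood is taken locally or at home.

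The cost is protocol and CRF wording plus one extra query and CRF entry per subject at a contact already planned. The downside is that later events will be mixed with subsequent care and harder to attribute, so they are best summarised separately from on-treatment events. No dose, clinical rule, sample size or alpha changes.

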12.3. Definition of an Adverse Event

An AE is any untoward medical occurrence in a clinical investigation subject administered a pharmaceutical product and which is not necessarily required to have a causal relationship with this treatment. An AE can therefore be any unfavorable and unintended sign, symptom, or disease temporally associated with the use of a medicinal product, whether or not considered related to the medicinal product. Examples of AEs include:

- Abnormal test findings
- Clinically significant symptoms and signs
- Changes in physical examination findings which are untoward and deemed clinically significant by the investigator.
- Allergy/hypersensitivity

The criteria for determining whether an abnormal objective test finding may be reported as an AE are as follows:

- Test result is associated with accompanying symptoms,
- Test result requires additional diagnostic testing or medical/surgical intervention,
- Test result leads to a change in study dosing or discontinuation from the study, significant additional concomitant drug treatment or other treatment, and/or
- Test result is considered to be an AE by the investigator or Sponsor.

Repeat of a test based on an abnormal result in the absence of the above conditions does not constitute an AE. Any abnormal test result determined to be an error does not require reporting as an AE.

A treatment-emergent AE (TEAE) is an AE that either commenced following initiation of study treatment or was present prior to study treatment but increased in frequency or severity following initiation of study treatment.

Standard medical terminology should be used in describing AEs. Informal descriptions should be avoided.

12.4. Serious Adverse Events

A serious adverse event (SAE) is any untoward medical occurrence at any dose which:

- Results in death
- Is life-threatening
- Requires inpatient hospitalization
- Results in persistent or significant disability
- Is another important medical event

Medical and scientific judgment is exercised in determining whether an event is an important medical event. An important medical event may not be immediately life-threatening and/or result in hospitalization or death. However, if it is determined that the event may jeopardize the subject or may require intervention to prevent an SAE outcome, the important medical event should be reported as serious. Examples of such events are intensive treatment in an emergency room or at home for allergic bronchospasm or blood dyscrasias or convulsions which do not result in hospitalization. All SAEs are reportable to the Sponsor within 24 hrs. of first awareness of the event by an investigator (see Section 12.9)

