Sample size:	
This is a parallel group adaptive design with one interim analysis after 6 subjects fulfilling final protocol GIR selection criteria in each study arm have completed their post-treatment success-failure determination. Depending on the comparison of the treatment and placebo failure rates the study will either be stopped with an early claim for treatment efficacy, or continued with either 3 or 6 additional subjects per study arm so that the final comparison of failure rates will be based on 9 or 12 subjects per study arm. This final sample size will be based on the outcome of the interim analysis.
 
The criteria for stopping early at 6 subjects per group or continuing to a final sample size of 9 or 12 subjects per group was designed so that the type 1 error is no larger than 0.025 for treatment = control failure rates at any failure rate value. The overall power for concluding that the treatment failure rate is less than control is over 98% if the placebo failure rate is at least 0.9 and the treatment rate is no more than 0.1, with early efficacy

	having a power of 66%. If the placebo failure rate is at least 0.95 and the treatment rate is no more than 0.05 then the chance for an early efficacy determination is 88%.
Subjects:	Hospitalized infant male or female patients with congenital hyperinsulinism less than 1 year of age at screening.
Inclusion Criteria:	
1) Patients diagnosed with hyperinsulinism
 
a. Biochemical; detectable insulin (i.e., ≥ 1 mU/L) at time of hypoglycemia (i.e. blood glucose < 50 mg/dL), and/or suppressed FFA, and/or suppressed BOHB and/or glycemc response to glucagon at time of hypoglycemia
 
and
 
2) Absolute necessity of intravenous glucose to prevent hypoglycemia as defined as attempts at weaning being unsuccessful.
 
a. Having failed diazoxide therapy.
 
b. Subject may be on diazoxide and/or octreotide, but these will be weaned off prior to randomization.
 
c. Subject may be on dextrose feeds.
 
3) Patient may be a participant in other study protocols such as observational studies, as long as no investigational intervention has taken place within 24 hours of screening.
 
4) Less than 12 months of age at screening.

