10. STUDY PROCEDURES

10.1. Screening Visit

Subjects will be screened to confirm they meet the selection criteria for the study. The investigator or study team member will obtain informed consent from each subject's parent/guardian in accordance with the procedures described below (see Section 16.3).

All subjects will be in-patients. Those less than 1 month of age or with unstable condition will be in the neonatal intensive care unit. As such, vital signs will be monitored continuously via cardiorespiratory monitoring. All enteric feedings will consist of FDA-approved, hospital-issued infant formula or breast milk provided by the mothers.

Subjects will undergo the following procedures to confirm they meet eligibility criteria for this study:

- Review medical history and medications
- Length and weight
- Blood pressure and pulse
- Physical examination
- Venous blood draws for tests as outlined in the Schedule of Activities (Table 5)
- Assessment of inclusion/exclusion criteria by Study investigator

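### The SAE list in Section 12.4 omits prolongation of an existing hospital stay although every subject is already an in-patient, so its hospitalization criterion does almost no work while adverse events are being collected.

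*Combined protocol and SAP*

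**What the plan says.** The seriousness list in Section 12.4 has five entries: death, threat to life, "Requires inpatient hospitalization", lasting or significant disability, and a fifth that reads "Is another important medical event". The fifth rests on medical and scientific judgment. It applies "if it is determined that the event may jeopardize the subject or may require intervention to prevent an SAE outcome".

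On the care setting, the Synopsis gives the population as "Hospitalized infant male or female patients with congenital hyperinsulinism less than 1 year of age at screening", and Section 10.1 says "All subjects will be in-patients". Section 11.3 adds "Heart rate and respiration will be measured continuously by cardiorespiratory monitoring", with daily recording until study treatment ends.

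On timing, Section 12.2 says that the adverse event reporting period "begins from the time informed consent is obtained through the last administration of the investigational product".

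On who decides, Section 12.1 has the investigator assess each adverse event against the FDA criteria and points to Section 12.4 for them. It adds that, in the sponsor's ongoing reviews, "any non-serious adverse event that is determined to be serious (according to the FDA definitions of an SAE) will be reported by the Sponsor", meaning that its seriousness is upgraded. The protocol does not reproduce the FDA definitions.

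**The concern.** The hospitalization criterion asks whether an event leads to admission. That is informative in outpatients. Here every subject is in hospital before the first dose and is expected to stay there through treatment. The corresponding consequence for an in-patient is a longer stay, and the list does not mention it.

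Several provisions depend on the SAE label:

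- notification of the sponsor within 24 hours (Sections 12.4 and 12.9);
- notification of the IRB, and expedited regulatory reports where they apply (Section 12.11);
- discontinuation of dosing for an SAE judged probably drug-related (Section 7.2);
- the incidence of SAEs, which is part of a secondary safety objective (Section 5.2, item 8).

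If an event that extends an infant's stay is not labelled serious at the site, it goes on the adverse event page of the CRF under Section 12.10, which sets no deadline.

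**Working it through.** No stated figure needs to be reproduced. The check sets the sections side by side.

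1. **Is prolongation a criterion anywhere?** It is not in Section 12.4. The definition of a device-related serious injury in Section 12.14 covers threat to life, permanent impairment or damage, and intervention to prevent these. It does not mention length of stay. No other section adds the criterion.

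2. **Can a new admission occur while adverse events are collected?** The window runs from consent to the last dose (Section 12.2). Subjects are hospitalized at entry (Synopsis) and are in-patients (Section 10.1). Continuous cardiorespiratory monitoring (Section 11.3) and glucose checks at least every three hours in open-label treatment (Section 10.2.3) fit hospital care throughout. A new admission within the window is therefore hardly possible.

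3. **Could one occur after the window?** Yes. Section 10.2.4 foresees a blood draw away from the site at 28 ± 14 days after the last dose, and Section 12.9 gives an outpatient subject as an example. By then reporting under Section 12.2 has closed. Only the rule on deaths in Section 12.9 expressly extends past treatment, to 4 weeks.

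4. **Which routes remain for an event that only lengthens the stay?** By construction it is not fatal, life-threatening or disabling. Two routes are left:
   - The important-medical-event entry, which is a judgment. Its illustrations in Section 12.4 are treatment in an emergency room or at home for events that do not lead to admission. They do not guide a decision about an infant already on a ward.
   - A sponsor upgrade under Section 12.1. This follows the site's report, whereas the 24-hour clock runs from the investigator's awareness of an SAE. Whether the upgrade covers prolongation depends on FDA text that the documents do not give.

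5. **How sensitive is the endpoint to one classification?** Planned evaluable numbers per arm are 6, 9 or 12 (Section 13.1). One infant classified differently moves an arm's SAE incidence by 1/n:
   - 1/6 = 16.7 percentage points
   - 1/9 = 11.1 percentage points
   - 1/12 = 8.3 percentage points

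   These figures apply to the randomized comparison in Period 2. The safety cohort includes everyone treated (Section 13.2), and non-evaluable subjects are replaced (Section 9.1), so arms may be somewhat larger and the steps somewhat smaller. The figures show sensitivity to a single reclassification. They do not say how many reclassifications to expect.

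**The case against.** The strongest reply is that the remaining routes are broad. An event that may endanger the infant, or that may need intervention to avert a serious outcome, is to be reported as serious whether or not it leads to admission. Life-threatening and disabling events qualify in any setting. The sponsor's review under Section 12.1 is central and does not depend on the investigator's choice. Events not called serious are still recorded and summarized (Sections 12.10 and 13.2.5.1). The criterion can also be read as asking whether the event by itself would need in-patient care, which an investigator could judge for an infant admitted for another reason.

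Much of this stands, and it rules out stronger conclusions that a reader might draw:

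- *Events that lengthen the stay are non-serious by definition.* Section 12.4 does not exclude them. A longer stay simply does not make an event serious on its own.
- *The criterion cannot operate, or is met by all events or by none.* The alternative reading above is possible, and admissions after treatment are conceivable.
- *Only the investigator can bring such an event in.* Section 12.1 gives the sponsor an independent route.
- *DSMB review is bypassed.* Section 15.4 describes periodic review of cumulative data and ties nothing to SAE classification.
- *SAE counts will differ between sites.* They may, because a judgment stands in for a criterion, but the documents give no evidence that they will.

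The reply does not supply the missing criterion. The alternative reading is not written down, and the sponsor's route comes later and refers to a definition outside the protocol, while sites are directed to Section 12.4.

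**Conclusion.** The gap is real and limited. The one hospitalization criterion does almost no work in the reporting window. An event whose only serious consequence is a longer stay depends on the important-medical-event judgment or on a later sponsor upgrade. What is affected is the timeliness and consistency of SAE reporting, the discontinuation rule that uses the label, and the SAE incidence endpoint.

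The number of events concerned cannot be derived from the documents. That every treated infant is an in-patient describes the setting and is not a measure of missed events.

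The conclusion assumes that subjects remain in hospital through the last dose, which the care-setting and monitoring provisions indicate although the outpatient example in Section 12.9 does not fit it. It assumes nothing about the content of the FDA definitions.

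**What to change.** In Section 12.4, and in the matching CRF item:

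- extend "Requires inpatient hospitalization" by the words *or prolongation of existing hospitalization*;
- state that the ongoing stay for congenital hyperinsulinism is not itself an SAE;
- state that prolongation is judged by whether the event itself extends the stay, as distinct from the underlying disease or the time taken to settle long-term management;
- align the list with the FDA definitions invoked in Section 12.1, so that site and sponsor apply the same text.

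The third item is needed because Period 3 has no fixed length below its 28-day maximum, so no reference stay exists against which to measure prolongation. Recording an expected stay at enrollment would be one way to support the judgment.

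The change affects reporting text only. It costs a few lines in the protocol and CRF and a few more SAE reports. Some judgment about what counts as prolongation will remain, but it will be exercised against a stated criterion.
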